## Endpoints

### 1.4 Primary endpoint

The primary endpoint for the ASPIRE trial is the difference in FPG at week 6 between the intervention arm that receives DNA-based diet advice and the control arm. This outcome has been chosen because it is the most sensitive indicator of impaired glucose regulation. Endpoints assessment will not be blind to the study intervention arm allocated.

## 1.5 Secondary endpoints

Secondary outcomes include differences at weeks 6, 12 and 26 between arms in the cross sectional values and changes from baseline of the variables listed below.

- Variables related to glucose regulation:
  - FPG at other time points
  - Plasma glucose at 120 minutes (P120) following 75g OGTT
  - Insulin resistance index (IRI) computed using the Homeostasis model assessment (HOMA) of beta cell function
  - c-peptide at 120 minutes following 75g OGTT
  - HbA1c
- Variables related to anthropometric measurements
  - Body weight
  - Body Mass Index (BMI)
  - Lean mass
  - Fat mass
  - Waist circumference
- Variables related to lipid profile
  - Total cholesterol
  - Fasting triglycerides
  - Low-density lipoprotein (LDL) cholesterol
  - High-density lipoprotein (HDL) cholesterol
- Variables related to clinical markers
  - Systolic Blood pressure (SBP)
  - Diastolic blood pressure (DBP)
- Dietary intake
  - Total energy intake
  - Carbohydrate intake
  - Fat intake
  - Saturated fat intake
  - Salt intake

- Vitamin D
- Vitamin B6
- Vitamin B12

## Study population

The study participants will be adults with impaired glucose regulation and fulfilling the following inclusion / exclusion criteria:

- Inclusion criteria
  - Provision of signed and dated informed consent form
  - Adults over 18 years of age
  - Impaired glucose regulation including IFG and IGT by FPG, OGTT or HbA1c criteria
  - Access to smartphone with an operating system of iOS 8.0 or above, or Android 4.0 or above.
- Exclusion criteria
  - Diabetic
  - Pregnant or planning pregnancy
  - Breastfeeding
  - Enrolled in other clinical trials
  - Have active malignancy or under investigation for malignancy
  - Severe visual impairment
  - Reduced manual dexterity
  - Use of psychiatric, anti-diabetic, and/or weight loss medication, and/or oral steroids
  - Bariatric surgery
  - History of illnesses that could interfere with the interpretation of the study results (e.g. HIV, Cushing syndrome, chronic kidney disease, chronic liver disease, hyperthyroidism, hereditary fructose intolerance, alcohol or substance abuse)
  - Unable to participate due to other factors, as assessed by the Chief Investigator

## Statistical considerations

### 1.6 Analysis population

#### - Intention to treat population (ITT)

Primary analyses will be conducted following the intention to treat (ITT) principle. All participants who are randomised into the study will be included in the ITT analysis and the analysis is conducted according to the randomised treatment arm.

#### - Per protocol population

In addition, the primary endpoint will be analysed with the Per Protocol population (PPP), which consists of those subjects in the ITT population who complete the study with no significant deviations from the planned protocol procedures. The exclusion will be as follows:

- Participants without impaired glucose regulation before inclusion [see definition page 6]
- Significant protocol deviation such as non respect of inclusion / exclusion criteria
- Pregnancy during follow-up
- Participants loss to follow-up or who withdrew consent

### 1.7 Data description

Data will be collected as described in protocol version 0.18 of 16/07/2018 and managed as described in the data management system version 0.5 of 01/10/2018. Data will be collected in electronic case report form (eCRF) completed by investigators. All data will be on the virtual machine for the medical statistician to work with, the data will be in the form of data extractions (i.e. not the CRFs). If the original CRFs are needed, they will be provided in a read only format.

#### 1.7.1 Recruitment and follow-up

Date of first and last study inclusion and of the last visit will be reported. A flow chart will be used to describe participants' flow. It will include the following information: number of persons screened, eligible, included, assessed at week 6 visit (see Figure 1). In addition, the number of participants screened, recruited, followed until study completion, lost to follow-up and who were withdrawn will be presented by month and intervention group in a table.

[figure not shown]
#### 1.7.2 Data summary

Collected data will be summarised without consideration for treatment group as follows:

- Quantitative data: maximum and minimum values, median and interquartile range (IQR);
- Qualitative data: count (n) and proportion (%);

In addition, for each variable, the proportion of missing data will be reported. This information will be reported using the following output table (Table 1 and 2).

**Figure 1.** Example of flowchart

**Table 1.** Example of output table for main continuous variables

Variable	Label	N	Missing	Min	Max	P25	P75	median

**Table 2.** Example of output table for main categorical variables

Variable	Label	N	Missing	n	%	Cumulative	
						n	%

### **1.7.3 Data review and exploration of outliers and problematic distribution**

The distribution of the main variables (e.g., FPG, triglyceride, cholesterol) will be assessed using published reference data. These distributions will be compared against a normal distribution using a quantile – quantile (QQ) plot. Skewness and kurtosis will be computed and additional assessment of normality may be conducted using the Kolmogorov-Smirnov test. Boxplot will be used to detect outliers.

Variables with outliers, missingness and/or problematic distribution will be reviewed with the some/all (where applicable) of the following members of the Trial Team:

- [name] (Dietitian)
- [name] (Research Nurse)
- [name] (Project Officer)
- [name] (Trial Manager)
- [name] (Chief Investigator)

### **1.8 Baseline characteristics and description of the study population**

Table 1 below lists the baseline variables of interest and presents the methods of derivation. The baseline variables will be summarised for each treatment arm using the mean with standard deviation (sd) for continuous data and count (n) with proportion (%) for categorical data. Statistical testing of between group imbalance in the baseline covariates will not be performed unless required for regulatory or publication reasons. A tabular presentation will be used to display the results.

Table 1. Baseline variables

Description	Definition	Type	Unit	Coding /derivation	CRF
Age		Num	Year	Number of years from date of birth (months : year)	Anonymised Randomisation log
Sex			N (%)		Screening enrolment log
HbA1c		Num	Mmol/mol		Visit2-CRF
Randomisation group	Intervention group assigned at randomization			Anonymised Randomisation log	
Height		m		Visit3-CRF	
Weight		Kg		Visit3-CRF	
Body mass index (BMI)		Kg/m 		Visit3-CRF	
BMI>30		N (%)		Visit3-CRF	
Fat body mass		Kg		Visit3-CRF	
Lean body mass		Kg		Visit3-CRF	
Waist circumference		cm		Visit3-CRF	
Systolic BP		mmHg		Visit3-CRF	
Diastolic BP		mmHg		Visit3-CRF	

Pulse		bpm		Visit3-CRF
Glucose t0	Plasma glucose at time 0 after 75g glucose load	Num	mM/L	Visit3-CRF
Glucose t120	Plasma glucose at 120' after 75g glucose load	Num	mM/L	Visit3-CRF
Insulin t120	Plasma Insulin at 120' after 75g glucose load		IU/L	Visit3-CRF
C-peptide t0	C-peptide at t0 after 75g glucose load		mM/L	Visit3-CRF
Total cholesterol			mM/L	Visit3-CRF
HDL-cholesterol			mM/L	Visit3-CRF
Non-HDL cholesterol			mM/L	Visit3-CRF
LDL cholesterol			mM/L	Visit3-CRF
Fasting TG			mM/L	Visit3-CRF

## 1.9 Analyses of quantitative data

Continuous outcomes will be compared between groups using the modified analysis of covariance (ANCOVA). This approach has been chosen because it is more powerful than other alternatives such as t-test.

A linear regression model will be used to analyse the association between post-intervention values of the outcomes with intervention arm adjusting for their baseline value, participant age and sex.

Let  $y_{it}$  denote the outcome value for individual  $i$  at time  $t$ ,  $x_i$  her covariates (e.g. sex, age) and  $d_i$  her intervention arm. The ANCOVA model is given by:

$$y_{it} = \beta_0 + \beta_1 y_{i0} + \beta_2 x_i + \gamma d_i + \varepsilon_{it}$$

An extension of the basic ANCOVA model will consider an interaction between the intervention indicator and the baseline values to test the assumption that the treatment effect varies with baseline status.

In addition, changes in continuous outcomes from baseline will be analysed using a linear regression model of the difference between the outcome value at visit and its baseline value. Using the same notation, the change model is

$$\Delta y_{it} = y_{it} - y_{i0} = \beta_0 + \beta_1 x_i + \gamma d_i + \varepsilon_{it}$$

Covariates will be centered in the analyses. Robust linear regression *lmrob* from the R package *robustbase* will be used for the ANCOVA analysis unless specified otherwise. It uses the MM-estimator to estimate the regression coefficient accounting for departure from normality of the outcomes.

Assessment of models' goodness of fit will include careful examination of residuals using graphical methods (scatter plot, boxplot and QQ plot) and detection of outliers. In addition, equality of the post-treatment variances will be tested using Levene's test.

## 1.10 Repeated measures analyses

Linear mixed model (LMM) will be used to analyse changes over time of continuous outcomes. Using the same notation ( $y_{it}$  for the outcome value for individual  $i$  at time  $t$ ,  $x_i$  the covariates, and  $d_i$  for the intervention arm), the following model will be used to model the change in  $y_{it}$

$$y_{it} = \beta_{0i} + \beta_{1i}t_{it} + \beta_{2i}X_i + \gamma_{0i}d_i + \eta_i + \varepsilon_{it}$$

LMM will be estimated using the REML method.

This model can be extended to account for non linearity in the time trend and for an interaction between time trend and intervention arm as follows:

$$y_{it} = \beta_{0i} + \beta_{1i}t_{it} + \beta_{2i}X_i + \gamma_{0i}d_i + \gamma_{1i}d_i t_{it} + \eta_i + \varepsilon_{it}$$

The assessment of the model's goodness of fit will be performed through graphical examination of the within-group residuals and random effects. It will include scatter plots of standardised residuals against fitted values as well as QQ plot and boxplot of standardised residuals and of random effects. The homoscedastic normal errors assumptions will be tested using the Shapiro-Wilks test and White's test of homoscedasticity of error variances.

## 1.11 Non-parametric model

For variables showing strong departure from normality, the non-parametric Mann Whitney Wilcoxon rank sum test (two groups) or the Kruskal and Wallis (to compare the three arms) will be used.

## 1.12 Missing data

Missing data will be imputed using the multiple imputation with chained equation (MICE) method using the other variables including outcomes variables if there is no evidence against the assumption of data missing at random. Missing at random refers to the fact that all factors related to the probability of a data being missing have been observed (they are missing completely at random meaning the missingness mechanism is completely stochastic). The cause for missing data will be carefully discussed with the investigator team to determine whether the missing at random assumption holds. The prediction of missing values will be performed after specifying a model from the variables distribution (e.g. linear regression model for normal distribution, logistic model for binary regression...). MICE will be performed using the R package mice with at least five imputed datasets.

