9.4 ANALYSIS OF PRIMARY AND SECONDARY OUTCOME MEASURES

Data will be analysed after all primary and secondary outcomes have been recorded for the last participant. The primary analysis will be conducted under the ITT principle using modified analysis of covariance (ANCOVA) (Yang & Tsiatis 2001). Raw and adjusted mean differences in PFG at week 6 between the intervention and control arm will be presented with 95% confidence interval (95%CI). The adjusted mean difference will be estimated using a linear regression model of week 6 FPG to baseline PFG and treatment arm adjusted for age and sex. An interaction of baseline FPG with the indicator for treatment arm will be included. PFG will be log transformed and variables will be centred.

The primary null hypothesis is no difference in W6 FPG between the intervention and the control arm. It will be rejected if the adjusted 95%CI of the mean difference does not include 0. The robustness of the results will be tested using PP analysis and two alternative models (repeated measure mixed model and non parametric model). Missing data will be imputed using the multiple imputation with chain equation (MICE) method if there is no evidence against the assumption of data missing at random.

The secondary analysis will be conducted under the ITT principle. The ANCOVA will be used to compare mean difference in FPG, weight, BMI, mass, waist, fasting lipids and blood pressure at the different time points (W6, W12 and W26). In addition, mixed models will be used to compare the overall changes in these outcomes over the all follow up period. Adequacy of the models will be assessed through residual plots and Shapiro-Wilk tests for normality. Non-parametric methods may be used in case of severe departure from normality. In the addition, logistic regression model will be used to compare the proportion of participants with IGR between the two arms. Change in dietary habits will be analysed using polytomous regression.

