## Study design

Open label randomised control trial. Participants will be randomised 1:1:1 to a) the control arm (n = 60) in which they will receive general health guidelines according to the NICE guidelines, b) the intervention arm (n = 60) in which they will receive DNA-based health guidelines via a genetic report, or to c) the exploratory arm (n = 60) in which they will receive DNA-based guidelines via the DnaNudge App.

The primary analysis will focus on the comparison between intervention arm and control arm.

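### Multiple imputation depends on a missing-at-random condition that has no criterion and no fallback, and no analysis covers data missing not at random

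*SAP*

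**What the plan says.** SAP section 1.12 makes MICE conditional: it runs "if there is no evidence against the assumption of data missing at random". Protocol section 9.4 sets the same condition: "Missing data will be imputed using the multiple imputation with chain equation (MICE) method if there is no evidence against the assumption".

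The SAP then explains the term twice. The main clause reads "Missing at random refers to the fact that all factors related to the probability of a data being missing have been observed", which describes missing at random (MAR). The parenthesis that follows reads "they are missing completely at random meaning the missingness mechanism is completely stochastic", which describes missing completely at random (MCAR).

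The causes of missing data are to be "carefully discussed with the investigator team to determine whether the missing at random assumption holds". No test, threshold or timing is attached. The design is described as "Open label randomised control trial", and SAP section 1.4 adds that endpoint assessment is not blind to arm.

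The number of imputations is set by "MICE will be performed using the R package mice with at least five imputed datasets".

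SAP section 1.6 puts every randomised participant in the ITT analysis. For the primary endpoint, SAP section 1.14 lists one sensitivity analysis, a non-parametric model. Protocol section 9.4 lists a per-protocol analysis, a repeated-measures mixed model and a non-parametric model. Neither document plans an analysis under missing not at random (MNAR).

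**The concern.** The condition decides whether the primary analysis is imputed at all, and it cannot be applied as a rule. Observed data can show that missingness depends on observed variables, which speaks against MCAR. They cannot separate MAR from MNAR. What remains is a judgement by people who know the allocation, with no criterion written down.

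The parenthesis adds a specific risk. An analyst who follows it would treat any observed predictor of dropout as evidence against the assumption and would switch MICE off, although MICE can handle that situation.

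Nothing is named to replace MICE if the condition fails. The planned regression would then most likely run on participants with a week-6 value, which is not the all-randomised set. Protocol section 4.5 makes selective loss plausible: significant non-compliance is a ground for discontinuation, clinical tests stop at withdrawal, and early withdrawals may be left out of the study. Compliance is not a covariate in the primary model.

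**Working it through.** **1. The plan's own figure: power.** Inputs from SAP section 1.14: difference 0.5 mmol/L (-0.6 against -0.1), post-intervention SD 0.6, correlation ρ from 0.4 to 0.6, 60 per arm. Two-sided alpha is 0.05. ANCOVA residual SD = 0.6·√(1-ρ²), SE = SD·√(2/n), and power ≈ Φ(0.5/SE - 1.96).

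| ρ | residual SD | n per arm | SE | power |
|---|---|---|---|---|
| 0.4 | 0.550 | 60 | 0.100 | 0.9987 |
| 0.6 | 0.480 | 60 | 0.088 | 0.9999 |
| 0.4 | 0.550 | 50 | 0.110 | 0.9951 |
| 0.6 | 0.480 | 50 | 0.096 | 0.9994 |

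The SAP's claim of power above 0.9 reproduces. It also survives analysing only 50 per arm, so losing imputation is not a power problem.

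**2. Missing rate.** Protocol section 9.3 raises 50 to 60 per arm, which allows for 10 of 60 = 16.7% lost. Part of that allowance is a 10% risk of diabetes over 12 months, whereas the primary endpoint is at 6 weeks. The week-6 rate is therefore unknown. The calculations below assume 10-30%.

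**3. What each reading of the condition does.**

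| Missingness depends on | Main clause (MAR) | Parenthesis (MCAR) | ANCOVA on observed cases |
|---|---|---|---|
| nothing | impute | impute | unbiased |
| baseline FPG, age or sex | impute | do not impute | close to unbiased (in the model) |
| observed variables outside the model | impute | do not impute | can be biased |
| the unseen week-6 value | do not impute, but undetectable from the data | do not impute, but undetectable from the data | can be biased |

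The two readings give different instructions in rows 2 and 3. Only row 3 does harm that MICE would remove. Row 4 needs a different tool.

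**4. Size of the possible bias.** Illustrative simulation: true difference -0.5 mmol/L, 16-18% of week-6 values missing, least-squares ANCOVA, and imputation using a correlated later FPG value.

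| Assumed mechanism | complete-case bias (mmol/L) | bias with imputation (mmol/L) |
|---|---|---|
| MCAR | 0.000 | 0.000 |
| MAR through baseline FPG | -0.002 | 0.000 |
| MAR through later FPG, differing by arm | -0.078 | 0.000 |
| MNAR | -0.099 | -0.053 |

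In the third row the bias is 0.078/0.5 = 16% of the target difference, or 0.078/0.105 = 0.74 of the estimate's standard deviation. In the fourth row imputation under MAR leaves 0.053/0.099 = 54% of the bias.

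**5. Number of imputations.** With total variance set to 1, the between-imputation variance is B = FMI/(1+1/m), and the Monte Carlo SD of the estimate in SE units is √(B/m). FMI, the fraction of missing information, is assumed to lie between 0.1 and 0.3.

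- m = 5: √(0.0833/5) = 0.129 to √(0.250/5) = 0.224.
- m = 50: √(0.0980/50) = 0.044 to √(0.294/50) = 0.077.

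Repeated imputation of simulated data with 16.7% missing gave a run-to-run SD of about 0.019 mmol/L at m = 5, 0.010 at m = 20 and 0.006 at m = 50. Average efficiency at m = 5 is 1/(1 + 0.167/5) = 0.968 of the maximum.

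**The case against.** The strongest reply has four parts.

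- **Definition.** The main clause is correct. A statistician who relies on it would not stop imputation because dropout was related to baseline FPG or age. This stands, and the fault is a contradictory parenthesis. A reader might infer that the SAP simply takes MAR to mean MCAR, but the main clause rules that out.
- **Discussion of causes.** Asking investigators why data are missing is a substantive assessment that a test on the data cannot replace. This also stands, and it is worth keeping as input to the sensitivity analysis. It does not supply a decision rule. A reader might also infer that the choice is made after unblinded outcomes have been seen. The documents do not say so: SAP section 1.7.2 summarises the data without regard to arm. They show only that the people consulted know the allocation and that the timing is not fixed.
- **Mixed model.** The planned mixed model uses all available visits without imputation and is valid under MAR, so it partly covers a mistaken switch-off. It is a robustness analysis in the protocol and a secondary analysis in SAP section 1.15. It adds little for someone who withdraws before week 6, and it does not address MNAR.
- **Limits of MICE.** Adherence is defined only from App activity in the exploratory arm (SAP, Exploratory analyses), so in the primary comparison MICE has only proxies such as dietary recall. Because clinical tests stop at withdrawal, later FPG helps only for participants who miss week 6 and return. This stands, and it is why imputation under MAR is not sufficient alone.

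**Conclusion.** The point holds as a defect in the rule for the primary analysis. The condition has no criterion, its definition contradicts itself, no fallback is named, and MNAR is not addressed. Complete-case analysis is the probable consequence of a failed condition, although neither document prescribes it.

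The stake is bias of unknown size and direction. In the illustrative simulation it was up to about 0.1 mmol/L against a target of 0.5. That figure rests on assumed mechanisms, about 17% missing and least squares in place of the planned robust regression, so the pattern is more reliable than the values.

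Three stronger readings are not supported:

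- that power is lost, since ANCOVA power stays at or above 0.995 with 50 per arm;
- that dropout related to baseline FPG, age or sex would distort the result, since all three are in the model;
- that the plan expects 12 of 60 lost, since raising 50 by 20% allows for 10 of 60.

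The number of imputations is a minor matter. Five is a floor, and its noise would change the conclusion only in a borderline result.

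**What to change.** In SAP section 1.12, with protocol section 9.4 brought into line:

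1. Make MICE under MAR unconditional for the primary ITT analysis. Impute by arm, because an interaction of arm with baseline FPG is to be tested. Name the predictors: baseline FPG, age, sex and FPG at other visits. The existing text allows other variables and outcomes but does not list them.
2. Delete the MCAR parenthesis and keep the main clause.
3. Prespecify a delta-adjusted (tipping-point) sensitivity analysis for MNAR. Shifting the imputed values of 10 of 60 participants in one arm by δ moves the difference by δ·10/60, so δ = 0.5 mmol/L moves it by 0.083. Discussion with the investigators can inform the range of δ. It should not decide whether imputation is done.
4. As a minor addition, set the number of imputations at about 20-50 and fix the seed.

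The cost is a few sentences in the SAP and minutes of computing.

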## Analysis of the primary endpoint

### 1.13 Derivation

*Measurement.* Under the protocol, participants are scheduled to have an OGTT at week 6 (visit 6, D42+/- 3 days). Plasma glucose at 0 minute will be measured after 12 hours fasting and before the 75g glucose load via an OGTT.

*Data transformation.* Available data from Arkadianos et al. suggests that PFG may not be normally distributed (see Annex). In the study by Arkadianos, post intervention PFG showed significant departure from normality with significant skewness (0.8, Agostinos test; p = 0.04). By contrast, no significant departure from normality was observed for PFG changes from baseline (Annex). Although the log transformation has been suggested in the literature, this transformation applied to Arkadianos data did not improve the normality of PFG distribution. Using the box-cox method, the best transformation was achieved with the boundary value of -2.

For this analysis, the preferred approach to handle departures from normality and outliers will be to use of robust statistical methods.

